Intensive Care of Elderly: What do They Wish for Themselves?

NCT05149040

Study protocol and Statistical Analysis Plan

06.06.2021 (version 3, IBM approval)

Project Description

1. Project Title

Treatment preferences of very elderly Norwegians in the event of acute life-threatening illness, and family members' ability to predict these treatment preferences: A self-administered survey.

2. Background

Very elderly patients (aged 80 years and older) are a large and steeply increasing patient population in western intensive care units (ICUs), but the overall benefit of intensive care for these patients remains controversial [1, 2]. Will ICU admission improve survival and quality of life, or will it prolong suffering and delay natural death? In case of medical uncertainty, crucial significance is attached to the patient's treatment preferences, but less than 1 in 4 very elderly ICU patients retain decision making capacity [3]. Therefore, information about the patient's likely will is frequently sought through a family conference.

Knowledge regarding the very elderly's life sustaining treatment (LST) preferences is scarce and has recently been rated as number two of top-ten research-topics by a broad panel of experts [4-6]. To our knowledge, so far no survey instrument for this purpose exists.

Research addressing the accuracy of proxy statements by family members has only shown low to moderate correlation [7, 8]. Both internal and external validity of the existing research addressing proxy accuracy is limited.

3. Study design

The overall goal of this project is to improve critically ill very elderly patients' ICU trajectories by bringing forth knowledge about their treatment preferences, their family members' ability to predict their wishes, and by directing attention to confounders of shared decision-making under uncertainty.

3.1. Research questions:

- Which preferences do very elderly people have regarding LST in the event of acute illness warranting ICU admission?
- How accurate can close family members predict the treatment preferences of a temporarily incapacitated very elderly patient with acute life-threatening illness?
- Are there factors that impact on very elderly patients' LST preferences, and on the ability of a close family member to predict these preferences?

3.2. Preregistration:

We plan to preregister the proposed study on www.ClinicalTrials.gov.

3.2. Protocol:

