3. 3 sentences on the consequences of the choice. The survival outcome estimates are based on short- and long-term outcome data from the VIP2- study data-set (table 2). The estimated quality of life regarding physical and cognitive function of ICU survivors aged ≥ 80 years is based on published data from Norway, Finland, the Netherlands and Canada [14-17], and a systematic review on cognitive impairment after intensive care [18]. Outcomes are identical for all vignettes, but in 50% of the questionnaires, the expected outcome is framed as mortality and in 50% as survival. The same framing is used for all four vignettes in each questionnaire.

ICU admission diagnosis	VIP-2 (May 2018-May 2019)					NIR (May 2018-May 2019)		
	N (%)	Survival (%)			N (%)	Survival (%)		
		ICU	30 d	6 m		ICU	30 d	1 y
Overall	3921 (100)	73	75	40	3069 (100)	86	67	47
ARF	941 (24)	75	76	34	951 (31)	84		
Sepsis	392 (14)	68	70	33	338 (11)	86		
Shock	540 (14)	72	71	34	737 (24)	88		
Acute surgery	541 (14)	80	82	45	614 (23)	86		
Trauma	233 (6)	69	70	30	215 (7)	85		
Neuro	190 (5)	68	68	30	153 (5)	87		

Table 2: Main admission diagnosis and survival of very elderly (≥ 80 år) ICU patients in Europe (VIP-2 data set, personal communication, [name], April 2021) and in Norway (NIR (Norwegian Intensive Care Registry), personal communication, [name], April 2021)

Furthermore, the survey covers items that may influence treatment preferences and proxy accuracy including: demographics, education, religion, previous experience with and / or communication about serious illness, comorbidity (Charlson Comorbidity Index, [19]), frailty (Clinical Frailty Scale, version 2, [20]), quality of life (EuroQol-5D-5L, registration ID: 30864, [21]) and projection (i.e. the proxy's own treatment preferences, [8]). Items were generated by a mapping review of the existing literature on elderly patients' treatment and end-of-life preferences and on proxy accuracy in general. Additional items were identified by discussions within the research group.

The questionnaires ask for the following free-text comments:

- Elaborating the treatment choice made after each scenario
- Expectations regarding family members contribution into the decisional process
- General comments

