We reduced and adjusted the “uncertain” and “the doctor should decide” answer categories to “wishing to not engage in the decision” after the pre-test in order to more precisely match the Norwegian regulations, where patient preferences are an important information into the medical decision process, but the ultimate decisional authority remains with the treating physician(s). Additional space for free-text comments is provided, and the respondents are asked to elaborate the reason for their preference. Moreover, we abstracted confidence into the choices made as an independent item and ask the participant to indicate for each scenario how certain they feel about their answer regarding treatment preference on a five-point Likert scale.

The pretest also revealed cases of assumed similarity, where the son/daughter apparently decided according to his/her own preferences which were different from the preferences of their elderly mother / father (red numbers in table 2). None of the respondents commented on unpleasant feelings when confronted with a question regarding life-threatening illness, but several both elderly persons and their adult children volunteered that they perceived the question to be relevant, important, and not sufficiently addressed yet.

An interesting observation from the pre-test was that respondents who opted for their physician to decide had less or no free text comments, compared to respondents who made a clear choice.

Pilot testing: We plan to assess the penultimate versions of the questionnaires (one for the very elderly person, and one for the potential proxy) for face validity, and clinical sensibility as well as to pilot them regarding relevance, flow, arrangement and time to complete.

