The above calculations are based on simple logistic regression, i.e., assuming that only *one* preference (from one patient vignette) is expressed for each participant. In practice, there will be four (correlated) preferences for each participant, and we will use statistical methods that take this into account (mixed-effects logistic regression instead of logistic regression). This will increase the statistical power; i.e., we will be able to detect lower odds ratios.

To assess the proxies' ability to predict their family member's preference, we will estimate the overall percentage agreement. Again, the absolute margin of error will be less than 7% (based on a 95% confidence interval). We will also estimate the agreement stratified by the family member's preference. Other measures of agreement (e.g., chance-corrected agreement) may also be calculated.

Furthermore, we will attempt to use (mixed-effects) logistic regression to examine variables associated with 'correct prediction' (and additionally stratified by the elderly's preference [23]). Only responses where the elderly has a preference ('wants ICU admission' or 'does not want ICU admission') will be included [24]. The analysis will only be carried out if enough elderly patients have a preference (we aim to have at least 5, and preferably 10 preferences, for each predictor variable that is included). The following predictors may be included:

Proxy's prediction, elderly's and proxy's certainty in the proxy's prediction of elderly's preference, proxy's preference, proxy's experience with intensive care, communication about end of life decisions, elderly's gender, proxy's gender, interaction between elderly's and proxy's gender, absolute difference in age between the elderly and the proxy, and proxy's assessment of elderly's frailty. (Predictors with high multicollinearity may be excluded.)

In all analyses where multiple responses are included for each participant or pair, we will use statistical methods that take this into account (e.g., mixed-effects logistic regression instead of ordinary logistic regression).

If free-text comments result in rich data, they will be analyzed by Systematic Text Condensation (STC) [25] and published separately.

4. Project organization

4.1. Research group:

Principal investigator:

[name] [name], SSAI and European Diploma of Intensive Care. Senior consultant at the Department of Surgical Services, Intensive Care Unit, Haukeland University Hospital.

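### The pooled 'correct prediction' model carries projection only as a main effect of the proxy's own preference, which does not measure it; a term for agreement with the elder's preference would

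*Combined protocol and SAP*

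**What the plan says.** The third research question (section 3.1) asks whether there are factors that bear "on the ability of a close family member to predict these preferences". Under 'Survey construction' (section 3.2, Protocol), the items that may influence accuracy include "projection (i.e. the proxy's own treatment preferences, [8". The proxy gives both a prediction and an own preference for each of four vignettes, with three response options: intensive care, no intensive care, or not engaging in the decision. Under 'Pre-testing': "The pretest also revealed cases of assumed similarity", meaning that some sons or daughters seemed to answer by their own, different wish.

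Under 'Analysis' the plan says "we will attempt to use (mixed-effects) logistic regression to examine variables associated with 'correct prediction", "and additionally stratified by the elderly's preference [23". The records are restricted: "Only responses where the elderly has a preference". One list of optional predictors serves both the pooled and the stratified analysis. It contains the proxy's prediction and the proxy's preference as separate entries, and its only interaction is between the two genders. No term or table compares the proxy's own preference with the elder's preference or with the prediction. The list closes with "Predictors with high multicollinearity may be excluded", without a threshold, an order of removal or a protected variable.

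**The concern.** Projection is a statement about agreement. A projecting proxy is right when his or her own wish happens to equal the elder's, and wrong when it does not. A main effect of the proxy's preference asks something else: whether proxies who want intensive care predict better or worse than proxies who do not. In the pooled data, gains among elders with one preference are offset by losses among elders with the other.

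The pooled coefficient could therefore be read as evidence that the proxy's own wish matters little, or matters in one direction only, in a sample where much of the prediction is projection. The survey was designed to measure this factor, and the pre-test pointed to it.

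**Working it through.** **The plan's own figures.** The plan gives no figure for projection. Its nearest figures reproduce: (0.7/0.3)/(0.5/0.5) = 2.33; power with 100 per group for 50% v 70% is 0.83 (two-sided 5% assumed); margin 1.96 × √(0.25/200) = 6.93%.

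**Assumptions (the documents give no rates).** A share s of predictions copies the proxy's own preference, and the rest are 70% accurate. The proxy's preference is independent of the elder's unless stated. Preferences are treated as two-level at first. Results are exact population values, not samples.

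**Accuracy by agreement.** When the preferences match, accuracy is s + 0.7(1 − s). When they differ, it is 0.7(1 − s).

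| s | match | differ | odds ratio, match v differ |
|---|---|---|---|
| 0 | 0.70 | 0.70 | 1.0 |
| 0.4 | 0.82 | 0.42 | (0.82/0.18)/(0.42/0.58) = 6.3 |
| 0.6 | 0.88 | 0.28 | (0.88/0.12)/(0.28/0.72) = 19 |
| 0.8 | 0.94 | 0.14 | (0.94/0.06)/(0.14/0.86) = 96 |

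**Pooled main effect, even split.** At s = 0.4, proxies wanting and not wanting intensive care are both right with probability 0.5 × 0.82 + 0.5 × 0.42 = 0.62. The odds ratio is 1.00. With both groups split 50/50 it is 1.00 at every s, with or without prediction in the model.

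**Pooled main effect, 30% of elders wanting intensive care, prediction left out.**
- s = 0.4: 0.3 × 0.82 + 0.7 × 0.42 = 0.54 against 0.7 × 0.82 + 0.3 × 0.42 = 0.70. The odds ratio is (0.54/0.46)/(0.70/0.30) = 0.50.
- s = 0.6: 0.46 against 0.70, odds ratio 0.37.
- s = 0.8: 0.38 against 0.70, odds ratio 0.26.

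If 70% of elders wanted intensive care, the two accuracies would swap and these would become their reciprocals, about 2.0, 2.7 and 3.8. The same projection then has the opposite sign.

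**Pooled main effect with prediction in the model, as listed.**
- 30% in both groups wanting intensive care, independent preferences: 0.89, 0.83 and 0.78 at s = 0.4, 0.6 and 0.8.
- 20% in both groups, independent: 0.84, 0.76 and 0.69.
- 30% in both groups, elder-proxy correlation 0.3: 1.26, 1.27, 1.26 and 1.25 at s = 0, 0.4, 0.6 and 0.8.
- 20% in both groups, correlation 0.3: 1.54, 1.58, 1.58 and 1.58 at the same four shares.

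Under a second assumed model, non-projecting proxies know the answer half the time and otherwise guess. The adjusted odds ratio then ranges from 0.58 to 1.56 for s from 0.3 to 0.9, and reaches 1.70 with no projection at all. The match term there is 4.3, 21 and 481 at s = 0.3, 0.6 and 0.9.

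**Stratified models without prediction.** Among elders who want intensive care, the odds ratio for proxy's preference is the match odds ratio. Among those who do not, it is its reciprocal: 6.3 / 0.16, 19 / 0.05 and 96 / 0.01. With prediction in the model these cannot be estimated, because correct means that the prediction equals the elder's preference. Within a stratum the prediction fixes the outcome, which is complete separation.

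**Collinearity.** With balanced, independent preferences, the correlation of prediction with own preference equals s, so the variance inflation factor is 1/(1 − s²): 1.2, 1.6 and 2.8 at s = 0.4, 0.6 and 0.8; 5.3 at 0.9; 10.3 at 0.95.

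**The case against.** The strongest reply is that the remedy is already planned. The sentence that introduces the pooled model also announces the analysis stratified by the elder's preference, and those models show projection as large effects of opposite sign. Sample size need not rule them out. The list has about 11 terms, so the plan's 5 to 10 preferences per predictor means 55 to 110. If half of the elders' answers state a preference and 30% of those want intensive care (assumptions), the smaller stratum has 4 × 0.5 × 0.3 = 0.6 responses per pair: 60 from 100 pairs and 120 from 200, ignoring clustering. This largely stands, and it confines the problem to the pooled model. It does not remove it. The single predictor list puts prediction into the stratified models, where they fail. The stratified models also split the sample, give no single estimate, and come with no planned comparison between strata.

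A reader might infer that the pooled coefficient is null however strong projection is. The figures do not support that: it moves well away from 1 when preferences are uneven and prediction is left out. The response also has three levels. With prediction left out, an even split and the second assumed model, 'not engage' against 'no intensive care' gives 0.54, 0.28 and 0.07 at s = 0.3, 0.6 and 0.9. The supportable statement is that the coefficient cannot be interpreted as projection.

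A reader might also infer that the collinearity rule will remove the variable. The rule is permissive, does not say which of two correlated predictors goes, and under common limits of 5 to 10 (an assumption) would apply only to very strong projection. It is a secondary point.

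Finally, the design is exploratory, this regression is one the team will attempt, and its predictors are optional. That is fair and limits the weight of the point.

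**Conclusion.** The point holds for the pooled model. The main effect of the proxy's preference does not measure projection. It is exactly 1.0 when both groups' preferences are evenly split. With prediction in the model it barely follows projection strength (about 0.7 to 1.6 in the settings tried under the first assumed model). With prediction left out and uneven preferences it moves, but its direction is set by which option is more common among elders. An agreement term rises from 1.0 to 6.3, 19 and 96 over the same range.

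The documents do not support the wider reading that the plan cannot detect projection: its stratified models can, once prediction is left out of them. The percentage agreement, overall and by the elder's preference, is unaffected. All odds ratios rest on assumed projection models, since the documents offer only eight complete pre-test pairs. The qualitative conclusion follows from what projection means and does not depend on those rates. The change is worth making before analysis because it is a better method at almost no cost.

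**What to change.** 1. In the pooled model, replace the main effect by a term for whether the proxy's own preference on that vignette agrees with the elder's. A three-level version (agrees, opposite, proxy prefers not to engage) settles the third response level. Alternatively, add the elder's preference and its interaction with the proxy's preference. With two levels, that interaction odds ratio is the ratio of the two stratum odds ratios, so it is the square of the match odds ratio.
2. Omit the proxy's prediction from the stratified models. Preferably report the agreement term from a pooled model without it as well: prediction is half of the outcome's definition, and a prediction of not engaging is always incorrect in the included records.
3. Exempt the projection term from the collinearity rule, and state that rule's threshold and order of removal.
4. Report how often the prediction equals the proxy's own preference among responses where proxy and elder differ, beside the error rate where they agree. The comparison is needed because ordinary error also produces such cases: in the two-level model above the first figure is 1 − 0.70 = 0.30 with no projection, and 0.58, 0.72 and 0.86 at s = 0.4, 0.6 and 0.8.

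The cost is analysis wording, one or two more model terms and one cross-tabulation of data already to be collected. The questionnaire and recruitment do not change.

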4.3. Plan / Milestones

Timeline	completed	completed	completed	Mai / June 2021	Juli / August 2021	September/ October 2021	November / December 2021
Survey development steps	Item generation	Item reduction Face / content validity assessment	Vignette feasibility (data dispersion)	Protocol write-up REC application	Pilot testing: - Relevance - Flow - Arrangement Clinical sensibility testing	Survey administration Data collection	Analysis Write-up
Approach	Mapping review Expert / laymen interviews	Expert / laymen interviews	Pre-test		Focus-groups (public engagement events) - Very elderly - Potential proxies	Recruitment of at least 400 outpatients	
Instrument version	0	1	1	2	2	3	

Table 4: study progress plan

4.3. Dissemination:

We plan to publish the results in a peer reviewed scientific medical journal.

Suggested authorship: [name], [name], [name], [name], [name], [name], [name], [name]

4.4. Plans for Implementation

The results of this project will be used to develop a clinical decision aid to guide intensivists when assessing very elderly patients with acute life-threatening illness, also incorporating illness severity scoring, frailty scoring, and assessment of capacity. The questionnaire if proven feasible in the proposed study will also serve as a template for further development of a European questionnaire for the conduction of an already proposed multinational survey [4].

5. User Involvement

Collaboration with the Norwegian Senior Advisory Organization, Senior Norge, has been formalized by cooperation with [name] who will assist at all steps of the research process, especially by checking comprehension and wording during survey and interview guide construction and by input from a lay perspective during data collection and dissemination of the results. The protocol has been presented to the user advisory board of the Western Norway Regional Health Authority, too, and we aim to recruit one more user representative into the research group.

The contribution by the user representative(s) and the public engagement events, i.e. focus group interviews during the questionnaire validation process, will be reported according to the GRIPP2-SF checklist [26].

6. Ethical considerations and data security

The project will be conducted in coherence with the principles for medical research as described by the Helsinki Declaration [27]. Ethical approval will be sought from The Regional Committee for Medical and Health Research Ethics. The Regional Ethical Committee as well as the data protection officer at Haukeland University Hospital have already assessed the questionnaire validation project (focus group interviews) and waived consent, since no patients are involved and no identifiable, health related or otherwise sensitive data of the informants will be stored (REK-ID: 276403, 25.5.2021).

Written informed consent will be obtained from all participants of the focus group interviews before pilot and clinical sensibility testing.

